## 1. STUDY DESIGN/SUMMARY

This is an open-label, multi-institution, phase Ib trial that evaluates the safety and tolerability and preliminary anti-tumor activity of fulvestrant, palbociclib and erdafitinib in patients with ER+/HER2-/FGFR-amplified metastatic breast cancer (MBC). Briefly, patient's eligibility criteria will include: post-menopausal women with metastatic ER+/HER2-/FGFR-amplified breast cancer without prior use of a CDK4/6 inhibitor or an FGFR inhibitor; ECOG performance status ≤1, normal baseline blood counts and chemistry laboratory profile; and no intercurrent uncontrolled illness. Treatment will be given until disease progression or unacceptable toxicity. To assess the anti-tumor effect of therapy, we will estimate the overall tumor burden at baseline to which subsequent measurements (performed every 8 weeks using the Solid Tumor Response Criteria [RECIST] v1.1) will be compared. Samples for pharmacokinetic and pharmacodynamic assessments will be obtained throughout the escalation portion of the study. A baseline biopsy of a metastatic site or archival tissue will be obtained in all patients for Next Generation Sequencing, to determine the therapeutic predictive role of *FGFR1-4*, *CCND1-2*, *CDK4* and *CDK6* amplifications, and *RB1* and *ESR1* mutations on clinical outcome. Plasma will also be serially obtained, initially for measurement of plasma cell-free tumor DNA (cfDNA) at baseline, at 4 weeks after treatment initiation and at disease progression. This would allow us to determine if the *FGFR1* amplification levels detected by cfDNA at 4 weeks is an early surrogate of response to the triple-combination proposed, and if the cfDNA results at disease progression show new genomic alterations potentially associated with resistance to CDK4/6 and FGFR inhibition.

## 2. OBJECTIVES AND ENDPOINTS

	Objectives	Endpoints
Primary	To determine the safety and tolerability of fulvestrant, palbociclib and erdafitinib in patients with ER+/HER2-/FGFR-amplified MBC	

Assessment of DLT during the first 4 weeks of treatment (cycle 1)

Determination of MTD

Secondary	

To determine the anti-tumor effect of fulvestrant, palbociclib and erdafitinib in patients with ER+/HER2-/FGFR-amplified MBC

Pharmacokinetic assessments of erdafitinib

	

Progression-free survival (PFS)

Overall response rate (ORR)

Clinical benefit rate (CBR; complete response + partial response + stable disease without disease progression at 6 months)

Pharmacokinetic (PK) assessments of erdafitinib

Correlative	

To determine pharmacodynamic biomarkers of FGFR inhibition

To determine the therapeutic predictive role of FGFR1-4, CCND1-2, CDK4 and CDK6 amplifications, and RB1 and ESR1 mutations on clinical outcome

To determine if the FGFR1 amplification levels by FISH and cfDNA is an early surrogate of response

To determine if the cfDNA results at disease progression show new genomic alterations potentially associated with resistance to CDK4/6 and FGFR inhibition.

	

Serial measurements of serum phosphate, calcium, vitamin D, parathyroid hormone (PTH), FGF23, sFGFR2, sFGFR3 and sFGFR4

FGFR1 FISH

Next Generation Sequencing (NGS) of baseline or archival tumor specimen

Plasma cfDNA at baseline, at 4 weeks and at disease progression

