### 3.3 Fibroblast Growth Factor Receptor-1 (FGFR1) in ER+ Breast Cancer

Somatic mutations in the FGFR pathway result in its aberrant activation, leading to cellular transformation, tumorigenesis and cancer progression. Several lines of evidence support a role for FGFRs in breast cancer.

FGFR1 amplification is present in about 15% of ER+ breast cancers, and is an independent predictor of overall survival in patients with ER+ breast cancer treated with tamoxifen. FGFR overexpression has been shown experimentally to mediate resistance to endocrine therapy through activation of the MAPK and PI3K pathways. About 30-40% of breast tumors with FGFR1 amplification also exhibit amplification of CCND1, FGF3/4/19 in chromosome 11q. This co-amplification is also associated with a reduction of patients' survival. Based on these data, several pharmaceutical companies have developed drugs targeting FGFR (Table 1), focusing their

Table 1. FGFR inhibitors

	JNJ-42756493 IC 50 (nM)	BGJ398 IC 50 (nM)	AZD4547 IC 50 (nM)	Lucitanib IC 50 (nM)
FGFR1	< 1	4.55	< 1	21
FGFR2	< 1	28.1	< 1	41
FGFR3	1.05	19.5	2.52	51
FGFR4	< 1	376	40.6	-----
FGFR3 (G697C)	1.90	28.8	5.25	-----
VEGFR1	-----	-----	-----	1
VEGFR2	-----	-----	-----	1.1
VEGFR3	-----	-----	-----	7.1
PDGFR $\alpha$	-----	-----	-----	0.43
PDGFR $\beta$	-----	-----	-----	0.26

clinical development on tumor subtypes with a high likelihood of dependence on FGFR pathway signaling. These include tumor types with *FGFR* amplifications, activating mutations and fusions.

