### 3.5 Rationale

Preliminary evidence demonstrates that specific FGFR blockade with compounds such as erdafitinib has a manageable tolerability profile with promising clinical activity. The optimal strategies for combining FGFR inhibition with other anticancer agents requires further research. Ongoing clinical trials with FGFR inhibitors are being enriched for tumors harboring specific *FGFR* mutations and amplifications presumed to be highly addicted to this pathway. To date, preliminary clinical data suggest that FGFR and/or FGF3/4/19 ligand amplification is associated with clinical benefit from FGFR inhibitors, suggesting these are biomarkers of tumor dependence on the FGF/FGFR pathway. Other data in support of this hypothesis are:

- In ER+ breast cancers, most *FGFR1* amplifications coexist with 11q amplification (*CCND1*, *FGF3/4/19*) and are associated with endocrine resistance
- Activation of *FGFR1* increases transcription and expression of cyclin D1 (not shown)
- In ER+/*FGFR1*-amplified breast cancer cells, an FGFR inhibitor does not inhibit pRb and a CDK4/6 inhibitor does not inhibit ERK or AKT (**Figure 2**)
- The combination of FGFR and CDK4 inhibitors has a synergistic effect against *FGFR1*-amplified breast cancer cells (**Figure 3 and 4**)

We hypothesize that *FGFR* amplification attenuates the response of ER+ breast cancers to the combination of ER and CDK4/6 antagonists. Thus, the triple combination of an antiestrogen plus a CDK4/6 and an FGFR inhibitor would have synergistic activity in ER+/*FGFR*-amplified MBC. In this application, we propose a clinical trial of fulvestrant, palbociclib with the FGFR tyrosine kinase inhibitor (TKI) erdafitinib in patients with ER+/ HER2-/*FGFR1*-4-amplified MBC. Within this proposal, we will perform a dose escalation phase Ib study to determine the safety and tolerability and preliminary anti-tumoral activity of the triple combination. Once the recommended dose for phase II trials (RDP2) is defined, a future open-label randomized phase II trial of fulvestrant and palbociclib with or without erdafitinib will be conducted.

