### 7.3 Agent Administration

The investigator will instruct the patient to take the study drugs as follows:

- Palbociclib: taken orally once daily, with food, for 21 days out of a 28-day cycle
- Erdafitinib: taken orally once daily, with or without food, at approximately the same time every day, in a 28-day cycle
- Fulvestrant: IM once every 28 days (except on cycle 1, when fulvestrant will also be administered on day 15). On the days that patients come in for clinic visit/ fulvestrant administration on even cycles (i.e. when tumor measurements or PKs are done), administration of palbociclib and erdafitinib should wait to be done in clinic.

A pill diary will be given to all patients enrolled in the study.

1 cycle = 28 days				
N of pts.	Dose Level	Fulvestrant (IM q28 days) §	Palbociclib* (PO daily x 21 out of 28 days)	Erdafitinib (PO daily)

3-6	3	500 mg	125 mg	8 mg
3-6	2	500 mg	125 mg	6 mg
3-6	1	500 mg	125 mg	5 mg
3-6	-1	500 mg	125 mg	4 mg

\* Palbociclib dose may be adjusted per standard of care clinical guidelines based on blood cell counts

§ On cycle 1, fulvestrant will also be administered on day 15 (loading dose)

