#### **10.5 Tissue Samples**

To determine the therapeutic predictive role of *FGFR1-4*, *CCND1-2*, *CDK4* and *CDK6* amplifications, and *RB1* and *ESR1* mutations on clinical outcome, FFPE tissue from primary tumor or from a metastatic tumor biopsy will be collected for *FGFR1* FISH analysis and Next Generation Sequencing in all patients enrolled in the study at the time of registration.

Collection of fresh frozen tissue from a metastasis at any point prior, during or after study drugs, is encouraged and desirable, especially in patients that achieve a good clinical response and subsequently have disease progression. The fresh biopsy will follow guidelines as listed in Section 10.4.3.

Summary of required tissue:

A) FFPE block from primary tumor or metastatic tumor biopsy, with adequate tissue to cut the tissue sections described in B) and C) below. Ideally, the invasive tumor area should be at least 5 mm x 5 mm and contain 20% tumor cellularity.

If participating institutions are not allowed to release FFPE blocks, the following should be prepared:

B) To perform *FGFR1* FISH for either pre-screening or central confirmation: 5 unstained slides cut at 4 microns each placed on charged (plus) slides. Do not bake on a hot plate (see 10.3.1).

C) To perform next generation sequencing cut in this order:

1. From a tumor block containing greater than 25 mm^2 of tumor with at least 20% tumor cellularity please provide:
  - a. 1 H&E (or an unstained 4 micron section on a plus [charged] slide) followed by,
  - b. 3 serial 20 micron peels placed in a DNase-RNAse free tube (wrapped in parafilm to exclude moisture) followed by,
  - c. 1 H&E (or an unstained 4 micron section on a plus [charged] slide)
  - d. Peels should be placed in the -80 freezer upon receipt until extraction is to take place.
2. Tumor blocks containing 5-20 mm^2 of tumor with at least 20% tumor cellularity please provide:
  - a) 1 H&E (or an unstained 4 micron section on a plus [charged] slide) followed by,
  - b) 6 serial 20 micron peels placed in a DNase-RNAse free tube (wrapped in parafilm to exclude moisture) followed by,
  - c) 1 H&E (or an unstained 4 micron section on a plus [charged] slide)
  - d) Peels should be placed in the -80 freezer upon receipt until extraction is to take place.

**All formalin-fixed paraffin embedded tissue and/or slides should be sent with a cold pack (except in winter months) to avoid melting that could compromise tissue analysis.**

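### With every patient on fulvestrant, palbociclib and erdafitinib and no comparator, the trial can describe marker-outcome associations but cannot determine the markers' predictive role

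*Combined protocol and SAP*

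**What the plan says.** **The objective.** Section 2 includes among the correlative objectives "To determine the therapeutic predictive role of" FGFR1-4, CCND1-2, CDK4 and CDK6 amplification and RB1 and ESR1 mutation on clinical outcome. The synopsis, Section 1 and Section 10.5 repeat it for the same list. Section 3.6.3 says the same of FGFR1 by FISH, and Section 3.6.4 adds the FGF3/4/19 amplifications.

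**The design.** Section 1 states: "This is an open-label, multi-institution, phase Ib trial that evaluates the safety and tolerability and preliminary anti-tumor activity of fulvestrant, palbociclib and erdafitinib". In the Section 7.3 dose table every level combines fulvestrant, palbociclib and erdafitinib, and only the erdafitinib dose changes. Section 17.2.1 mentions arms in passing, but no second arm is defined anywhere.

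**The background.** Section 3.3 says that FGFR1 amplification "is an independent predictor of overall survival in patients with ER+ breast cancer treated with tamoxifen". Of FGFR1 amplified together with the 11q genes it says: "This co-amplification is also associated with a reduction of patients' survival". Section 3.5 hypothesises that FGFR "amplification attenuates the response of ER+ breast cancers to the combination of ER and CDK4/6 antagonists".

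**The later trial.** Section 3.5 says that, once the phase II dose is known, "a future open-label randomized phase II trial of fulvestrant and palbociclib with or without erdafitinib will be conducted".

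**The analysis.** Section 17 has no analysis for the marker objective. Section 17.2.2 covers ORR, CBR and PFS with 95% confidence intervals and Kaplan-Meier curves, and then pharmacokinetics.

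**The concern.** A marker is predictive of benefit from a drug when the effect of that drug differs by marker status. To show this, outcomes must be compared with and without the drug, within each marker group. Here nobody is assigned to go without any of the three drugs. A difference in outcome between marker-positive and marker-negative patients therefore mixes three things: the general course of the disease, resistance or sensitivity to the fulvestrant-palbociclib backbone, and any differential effect of erdafitinib.

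The protocol gives reasons to expect the first two. It ties FGFR1 and 11q amplification to survival outside any erdafitinib comparison. It expects FGFR amplification to blunt the backbone. In Section 3.6.4 it introduces RB1 loss and ESR1 mutation as mechanisms of resistance to CDK4/6 inhibition and endocrine therapy.

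At stake is how the correlative results are interpreted. The error can run either way: a marker that only tracks outcome could be reported as predictive, or a truly predictive one dismissed.

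**Working it through.** **1. The plan's own figures.** None is given for this objective: no effect size, alpha, power or multiplicity rule. The operating characteristic in Section 17.2.1 concerns tolerability, the probability of at least 15 tolerant patients out of 20. It reproduces from the exact binomial (for example 0.804 against the stated 0.80 at a true rate of 0.8). It does not bear on the markers.

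**2. Number of markers.** FGFR1-4 (4) + CCND1-2 (2) + CDK4 + CDK6 + RB1 + ESR1 = 10. Adding FGF3, FGF4 and FGF19 from Section 3.6.4 gives 13.

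**3. Is the interaction identified?** Take erdafitinib as the example, and define:
- H0: hazard ratio, marker-positive versus marker-negative, on fulvestrant plus palbociclib alone;
- R: erdafitinib hazard ratio in marker-positive patients divided by that in marker-negative patients (R = 1 means not predictive);
- H1: hazard ratio, marker-positive versus marker-negative, on the triplet.

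Then H1 = H0 × R. The trial estimates H1 only. With assumed values:

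| Observed H1 | H0 | R = H1/H0 | Reading |
|---|---|---|---|
| 1.0 | 1.0 | 1.0 | not predictive |
| 1.0 | 1.5 | 0.67 | more benefit if marker-positive |
| 1.0 | 2.0 | 0.50 | much more benefit if marker-positive |
| 1.5 | 1.0 | 1.5 | less benefit if marker-positive |
| 1.5 | 1.5 | 1.0 | not predictive |
| 1.5 | 2.0 | 0.75 | more benefit if marker-positive |

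Even the direction of R is undetermined. More patients on the triplet would sharpen H1 but would not separate H0 from R. The same algebra holds for palbociclib and fulvestrant.

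**4. Could response rate avoid this?** No. The backbone drugs produce responses without erdafitinib: 19.2% for fulvestrant 250 mg (Section 3.1.1) and 42.1% for palbociclib plus letrozole (Section 3.2.1). A response on the triplet cannot be credited to erdafitinib. Patients who stop erdafitinib and continue the other two drugs (Section 8.5) are not a comparator either, because they are selected by events after treatment starts.

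**5. What the sample size allows for plain association.** The synopsis gives 26 to 35 patients. By the Schoenfeld approximation, power = Φ(√[D·m(1−m)]·|ln HR| − 1.96), with D events and marker prevalence m. I assume a hazard ratio of 0.5, two-sided 5%, and an event in every patient, which is optimistic:
- m = 50%: 42% for D = 26 and 54% for D = 35;
- m = 15%: 31% for D = 35.

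**6. What an interaction test would need.** With 1:1 allocation with and without erdafitinib, 80% power and two-sided 5%, events = (1.96 + 0.84)² / [0.25·m(1−m)·(ln R)²]. For R = 0.5 this gives 262 events at m = 50% and 513 at m = 15%. These are scale illustrations on assumed values.

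**7. Multiplicity, as a hypothetical.** If each marker were tested at 5% and the tests were independent, the chance of at least one false association would be 1 − 0.95^10 = 0.40, or 1 − 0.95^13 = 0.49. The plan specifies no such tests.

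**The case against.** The strongest reply is that the word is used loosely and the plan already limits the claim. The objective is correlative, the lowest tier. The synopsis places tissue and plasma collection under exploratory assessments. Section 1 calls the anti-tumour evaluation preliminary, and Section 3.5 leaves the randomised comparison to a later trial. Enrolling both amplified and non-amplified patients (Section 4.1.6) does allow outcome to be compared by marker status on the triplet. All of this stands, and it keeps the point minor. It does not rescue the wording, which promises to determine a predictive role and appears in several sections.

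A second reply is that the objective does not name erdafitinib, and that RB1 and ESR1 relate more naturally to palbociclib and endocrine therapy. This is right and matters for the remedy. The missing contrast affects all three drugs, and a trial that varies only erdafitinib would supply just one of them.

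A third reply is that the multiplicity figure describes an analysis nobody has planned. This also stands. Section 17 sets no marker tests and no 5% level. Independence conflicts with Section 3.3, where about 30-40% of FGFR1-amplified tumours also carry the 11q amplification. Section 10.5.1 notes the low prevalence of FGFR2-4 amplification, so some tests might have almost no positive patients. Dependence and sparse markers would generally pull the figure below 40%.

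**Conclusion.** The objective is wrong as written, with minor consequences. No treatment-by-marker interaction is estimable for any of the three drugs, at any sample size, because there is no comparator. This rests on the design alone. The hazard ratios, prevalences and event counts above are assumptions that illustrate it. DLT, MTD and tolerability conclusions are unaffected.

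Four stronger readings are tempting, and the documents do not support them.
- A reader might infer that the protocol calls FGFR1 amplification prognostic. Its body text does not. It reports a link to overall survival under tamoxifen and otherwise speaks mainly of endocrine resistance. Tamoxifen-treated patients alone cannot separate prognosis from tamoxifen resistance, though either would confound the reading here. The survival evidence also covers only FGFR1 and the 11q co-amplification; for the other markers the missing comparator is sufficient argument.
- A reader might take 40% as this trial's false-positive rate. It is a hypothetical that assumes independent tests at 5%.
- A reader might infer that these marker results will select patients for the phase II. No section says so; Section 17.2.1 carries forward dose and tolerability.
- A reader might infer that the planned phase II would settle the predictive role of every marker. Both of its arms receive fulvestrant and palbociclib, so it could address erdafitinib benefit only.

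**What to change.** 1. In the synopsis and Sections 1, 2, 3.6.3, 3.6.4 and 10.5, restate the objective as: *to describe the association of these alterations with outcome under the triplet (hypothesis-generating)*. Use one marker list throughout, so that ten or thirteen is settled.
2. Add a short paragraph to Section 17: marker associations will be reported as estimates with 95% confidence intervals, with the number of markers examined and without any claim of prediction.
3. State that marker prediction of erdafitinib benefit can be tested only in a randomised comparison with and without erdafitinib, such as the planned phase II, and that this trial would not establish prediction of palbociclib or fulvestrant benefit.
4. If a multiplicity figure is cited (about 40% for 10 tests, 49% for 13), label it a hypothetical illustration that assumes independent tests at 5%, which the plan does not specify.

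The cost is an amendment of wording and one analysis paragraph, with no new patients, samples or assays. The downside is a more modest stated aim.

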### 3. BACKGROUND

#### 3.1 Estrogen receptor-positive (ER+) Breast Cancer

Despite advances in early detection and therapeutic options, unresectable or metastatic breast cancer remains incurable and is one of the leading causes of cancer-related mortality. Breast cancer is a molecularly heterogeneous disease with three distinct molecular subtypes. The first group is characterized by estrogen receptor (ER) expression positivity and/or progesterone receptor (PgR) positivity with the absence of over-expression or amplification of HER2. The second group is characterized by over-expression or amplification of HER2, with more than half of these tumors being positive (+) for expression of ER/PgR. The third group lacks detectable ER and PgR, and overexpression of HER2, and is thus referred to as triple-negative breast cancer. Approximately 65% of newly diagnosed breast cancers are ER/PgR+ and HER2-negative (also referred to as luminal tumors), while an additional 20% of newly diagnosed cases are HER2+. ER-targeted drugs, specifically drugs that antagonize estrogen binding to the ER (tamoxifen), drugs that block estrogen biosynthesis (non-steroidal and steroid aromatase inhibitors [AI] - only effective in postmenopausal patients), and drugs that antagonize and downregulate the ER (fulvestrant), have been the mainstay of systemic treatment for patients with both localized and metastatic ER/PgR+ breast cancers.

Fulvestrant is the most recent addition to the armamentarium of hormonal therapies available to treat these patients. However, acquired resistance (and occasionally primary resistance) to anti-estrogen therapy universally develops in patients with ER+ MBC. Interestingly, even after acquired resistance develops, breast cancer cells appear to still depend on low-level ER activity in addition to signaling through sometimes acquired oncogenic signaling pathways. In addition, in patients initially diagnosed with ER/PgR+ localized breast cancer who later recur, tumors usually demonstrate some degree of resistance to antiestrogen therapy at the time of recurrence. Therefore, improving the efficacy of endocrine therapy would be of great benefit to patients with breast cancer and represents a large unmet medical need.

##### 3.1.1 Fulvestrant

Fulvestrant (a selective estrogen receptor downregulator or SERD) is currently a standard of care hormonal therapy option in patients with ER+ MBC. Fulvestrant has an affinity for ER comparable to estradiol. It blocks the trophic actions of estrogens without any partial agonist (estrogen-like) activity, and is currently indicated for the treatment of ER+ MBC in postmenopausal women with disease progression following primary antiestrogen therapy. Clinical trials in postmenopausal women with primary breast cancer have shown that fulvestrant significantly downregulates tumor ER protein levels compared with placebo. There was also a significant decrease in PgR expression consistent with inhibition of ER $\alpha$  transcription. Further, treatment with fulvestrant inhibits tumor cell proliferation as measured by Ki67 immunohistochemistry.

Two phase III clinical trials were completed in a total of 851 postmenopausal women with breast cancer who had disease recurrence on or after adjuvant endocrine therapy or progression following endocrine therapy for advanced disease. These trials compared the safety and efficacy of monthly administration of fulvestrant 250 mg vs. the non-steroidal AI anastrozole at 1 mg/daily. Monthly 250 mg fulvestrant was at least as effective as anastrozole in terms of PFS, OR, and time to death. The combined data showed an objective response rate for fulvestrant of 19.2% compared with 16.5% for anastrozole. The median time to death was 27.4 months for patients treated with fulvestrant and 27.6 months for patients treated with anastrozole. The hazard ratio of fulvestrant 250 mg to anastrozole for time to death was 1.01 (95% CI 0.86 to 1.19).

Doses of fulvestrant higher than 250 mg have greater pharmacodynamic activity against the ER pathway. Thus, a 500 mg monthly dose after an initial load is now the FDA-approved standard of care. A phase III clinical trial (CONFIRM) was completed in 736 postmenopausal women with breast cancer who had disease recurrence on or after adjuvant endocrine therapy or progression following endocrine therapy for advanced disease. The study included 423 patients whose disease had recurred or progressed during antiestrogen therapy and 313 patients whose disease had recurred or progressed during AI therapy. This trial compared the efficacy and safety of fulvestrant 500 mg (n=362) vs. 250 mg (n=374). PFS for fulvestrant 500 mg was 6.5 months compared to 5.5 months for fulvestrant 250 mg. Overall survival data from the time of final analysis showed a median time to death of 26.4 months for fulvestrant 500 mg vs. 22.3 months for fulvestrant 250 mg [HR (95%CI) 0.81 (0.69, 0.96), p=0.016].

The routes of elimination for fulvestrant include combinations of a number of possible biotransformation pathways analogous to those of endogenous steroids, including oxidation, aromatic hydroxylation, and conjugation with glucuronic acid and/or sulphate. There are no known drug-drug interactions. Fulvestrant does not significantly inhibit any of the major CYP isoenzymes, including CYP 1A2, 2C9, 2C19, 2D6, and 3A4 *in vitro*, and studies of co-administration of fulvestrant with midazolam indicate that therapeutic doses of fulvestrant have no inhibitory effects on CYP 3A4 or alter blood levels of drugs metabolized by that enzyme. Although fulvestrant is partly metabolized by CYP 3A4, a clinical study with rifampin, an inducer of CYP 3A4, showed no effect on the pharmacokinetics (PK) of fulvestrant. Also results from a healthy volunteer study with ketoconazole, a potent inhibitor of CYP3A4, indicated that ketoconazole had no effect on the PK of fulvestrant, and therefore, dosage adjustment is not necessary in patients with co-prescribed CYP 3A4 inhibitors or inducers.

